#### 10.1.2 Definitions and Investigator Assessments

##### 10.1.2.1 Adverse Events

An AE is defined as any untoward medical occurrence in a patient regardless of causal relationship with study drug. An AE can therefore be any clinically significant unfavorable and unintended sign, symptom, or disease that occurs in the study whether or not the AE is related to the study drug. An AE can be a new condition or worsening of a pre-existing condition.

##### 10.1.2.2 Clinical Significance

The investigator will review all patient-reported events, laboratory and other test results and use clinical judgement to identify events that are clinically significant.

Clinical significance is defined as any abnormal finding that results in further clinical investigation(s), treatment(s), or the diagnosis of a new condition. Patient-reported events and protocol-mandated laboratory values, vital signs, and physical examination findings can be considered clinically significant (i.e., an AE) if there is a deterioration as compared to baseline. Examples of clinically significant worsening from baseline could include, but is not limited to, events causing withdrawal from the study and events requiring medical intervention outside of the study or are otherwise judged relevant by the investigator.

#### 10.1.2.3 Serious Adverse Events

Each TEAE must be classified by the investigator as either serious or non-serious. This assessment is made independently of severity assessment ([Section 10.1.2.4](#)). For example, the development of a severe rash may not meet serious criteria as defined below and therefore would be considered a severe, non-serious AE.

An SAE is any untoward medical occurrence that:

- Results in **death**
- Is **life-threatening** means that the patient, in the opinion of the investigator, was at immediate risk of death at the time of the event. This does not include an event which hypothetically may have caused death if it was more severe
- Requires or prolongs **inpatient hospitalization**. Inpatient hospitalization is defined as any stay in the hospital of more than 24 hours, or any admission to a hospital ward or unit as an inpatient.
  - Hospitalizations for procedures that were planned prior to study participation are not considered SAEs.
- Results in persistent or significant **disability/incapacity**. Disability means a substantial disruption of a person's ability to conduct normal life functions
- The AE results in a **congenital anomaly/birth defect**
- **Is an important medical event**. The investigator should apply medical and scientific judgement to assess whether an AE should be classified as a serious AE due to medical significance, even if no other seriousness criteria is met

As a general guideline, medically important events may not be immediately life-threatening or result in death or hospitalization but may jeopardize the patient or may require intervention to prevent one of the outcomes listed in the definitions above

Example: Allergic bronchospasm requiring intensive treatment in an emergency room

#### 10.1.2.4 Investigator Assessment of Severity

Severity is a measure of intensity, whereas seriousness is defined by criteria outlined in [Section 10.1.2.3](#).

Severity assessments are based on the intensity of the event in relation to expectation.

The Investigator will assess the intensity of AEs based on the Common Terminology Criteria for Adverse Events (CTCAE) Version 5.0 grading system as follows:

[https://ctep.cancer.gov/protocolDevelopment/electronic\\_applications/docs/CTCAE\\_v5\\_Quick\\_Reference\\_8.5x11.pdf](https://ctep.cancer.gov/protocolDevelopment/electronic_applications/docs/CTCAE_v5_Quick_Reference_8.5x11.pdf)

- Grade 1: Mild; asymptomatic or mild symptoms, clinical or diagnostic observations only; intervention not indicated.
- Grade 2: Moderate; minimal, local or noninvasive intervention indicated; limiting age appropriate instrumental activities of daily living.
- Grade 3: Severe or medically significant but not immediately life-threatening; hospitalization or prolongation of hospitalization indicated; disabling; limiting self-care activities of daily living.
- Grade 4: Life-threatening consequences; urgent intervention indicated.
- Grade 5: Death related to AE.

An AE of severe intensity need not necessarily be considered serious. For example, nausea that persists for several hours may be considered severe nausea, but not meet any seriousness criteria, and therefore would be assessed as a severe non-serious AE. CTCAE Grades 4 (life-threatening) and 5 (death) should always be reported as SAEs.

#### **10.1.2.5 Investigator Assessment of Causality**

The investigator determines the causality of all AEs to the study drug using medical judgment and considering all relevant factors such as (but not limited to) the underlying study indication, coexisting disease, concomitant medication, relevant history, pattern of the AE, temporal relationship to the study drug, and de-challenge or re-challenge information. The causality assessment of the AE/SAE is to be made as follows.

#### **Related to study drug (possibly, probably, or definitely related)**

Based on medical judgment, there is a reasonable possibility that the study drug caused the event. This includes situations where one or more of the following criteria apply:

- The event follows a reasonable temporal sequence from administration of study drug
- The event could not be reasonably attributed to the known characteristics of the patient's clinical state, environmental or toxic factors, or other modes of therapy administered to the patient
- The event follows a known pattern of response to study drug
- The event disappears or decreases on cessation or reduction in dose of the study drug (positive de-challenge). It should be noted that in some situations an AE will not

disappear or decrease in intensity upon discontinuation of study drug despite other clear indications of relatedness

- The event reappears or worsens when the study drug is re-administered (positive re-challenge)

#### **Unrelated to study drug (unlikely or unrelated)**

Based on medical judgment there is no reasonable possibility that the study drug caused the event. This includes situations where one or more of the following criteria apply:

- The event does not follow a reasonable temporal sequence from administration of study drug
- The event could be reasonably attributed to the known characteristics of the patient's clinical state, concurrent illness, environment or toxic factors, or other modes of therapy administered to the patient
- The event does not follow a known pattern of response to study drug
- The event does not disappear or decrease on cessation or reduction in dose of the study drug, and it does not reappear or worsen when the study drug is re-administered

Default assessments of the related category without supportive evidence for a causal relationship to study drug is generally uninformative and does not contribute meaningfully to the development of the safety profile of the drug or to patient safety.

#### **10.1.3 Recording of Adverse Events**

Patients must be carefully monitored for the development of any AEs during the safety reporting period.

All observed AEs and any AEs that are spontaneously reported by the patient/caregiver will be recorded by the investigator. For all AEs, the severity, seriousness, and causality to study drug for each AE as outlined in [Section 10.1.2](#) will be assessed and recorded in the eCRF.

Any AE assessed as serious must be reported within 24 hours of site awareness.

Any SAEs or AEs that lead to permanent discontinuation of study drug that are unresolved at the time of the last study visit will be followed up by the investigator until resolution or stabilization. Following the last study visit, the Sponsor will provide forms for reporting additional information for any patient with ongoing SAEs or AEs that led to permanent discontinuation of study drug. Albireo retains the right to request additional information for any patient with ongoing AE(s) or SAE(s) at the end of the study.

Treatment-emergent AEs are defined as any AE that occurs after first dose of study drug. All SAEs that occur in the Screening Period, i.e. after enrollment and prior to first dose of study drug, will be collected as non-treatment emergent SAEs.

If there is a clinically significant deterioration of a laboratory value/vital sign or other routine study assessment that is associated with a diagnosis, the clinical diagnosis will be reported

as an AE and the associated signs and symptoms will be considered additional information unless the sign or symptom is more severe than expected given the diagnosis. For example, in a patient diagnosed with hepatitis during the safety reporting period, hepatitis would be considered the AE. Signs and symptoms of abdominal pain, vomiting, and elevated ALT and AST would not be reported separately unless, in the opinion of the investigator, one of these signs or symptoms is more severe than expected and therefore a separate AE assessment is indicated.

#### **10.1.4 Recording and Reporting of Serious Adverse Events**

Every SAE, regardless of severity and causality, that occurs during the safety reporting period must be reported by the investigator or delegate in the SAE eCRF within 24 hours of site awareness.

The SAE report is to include at least the following information:

- Patient identification information (study number, site number, and date of birth as per local country requirements for data protection)
- The event term. Provide the diagnosis term, if known. If a diagnosis is unknown, provide the signs/symptoms. Update the event term once a diagnosis is known
- Date of onset
- The action(s) taken to treat the event (i.e. treatment medications, temporary discontinuation)
- The event outcome
- Seriousness criteria
- The relationship of the event to the study drug or to the study procedure (i.e. the investigator's assessment of causality)
- A brief narrative of the clinical course of the SAE

Follow up reports to already reported SAEs should contain any new information or query responses and must be documented on the SAE eCRF using the same process and timelines as for the initial SAE report.

If the SAE eCRF is not accessible, a hardcopy SAE form should be completed within 24 hours of the site becoming aware of the event and faxed or emailed to the address on the form and later entered in the eCRF when it becomes accessible.

#### **10.1.5 24-Hour Emergency Contact**

In a study-related medical emergency situation when the assigned medical monitors for the study cannot be reached by a caller, an on-call physician can be reached 24 hours per day, 7 days per week, via the call center.

#### **Reporting of Expedited Safety Reports**

A suspected unexpected serious adverse reaction (SUSAR) is an SAE that occurs in a patient, the nature or severity of which is not expected per the applicable product information (i.e. the investigator brochure).

The Sponsor and/or its designee are responsible for reporting of SUSARs to regulatory authorities, central ethics committees and investigators within required timelines.

The investigator is responsible for submitting required safety information to their local Institutional Review Board (IRB) or IEC per local regulations. This information includes, but is not limited to, any safety alert letter received from the sponsor.

#### **10.1.5.1 Special Situations**

Certain safety events are defined by regulatory authorities as Special Situations and require reporting. These Special Situations include:

- Overdose of study medication (See [Section 10.2.8](#))
- Suspected abuse/misuse of study medication
- Medication error involving the study medication
- Drug-drug interaction
- Pregnancy (See [Section 10.2.9](#))

Special Situations should be reported on the Special Situations eCRF, whether or not they result in an AE/SAE. If a Special Situation results in an AE or SAE, the event also should be reported on the AE/SAE eCRF following the process described in [Section 10.1.2](#).

### **10.2 Laboratory Values/Vital Signs/Physical Examinations and Other Safety Assessments**

#### **10.2.1 Laboratory Assessments**

Samples will be collected for clinical chemistry, hematology, and urinalysis testing at the time points specified in [Table 1](#). The parameters assessed are presented in [Table 4](#).

At screening, alkaline phosphatase will be fractionated (liver, bone, and intestinal isoenzymes) for patients  $\geq$  age 18 at the time of enrollment. If alkaline phosphatase is elevated during the treatment period, isoenzymes can be re-measured to assist in evaluation of the alkaline phosphatase elevation.

Blood for AFP measurement will be drawn at randomization (Study Day 1) and Week 24/EOT visits. Blood for measurement of fat-soluble vitamin levels including vitamins A and E, and 25-hydroxy vitamin D will be drawn at Screening Visit 1, randomization (Study Day 1), Week 12, and Week 24/EOT visits. Blood for INR (surrogate for vitamin K) will be drawn at Screening Visit 1, randomization (Study Day 1), Week 4 to 24/EOT, and Safety Follow-up visits. Patients will fast (water intake only is permissible) for at least 4 hours prior to the collection of samples for vitamin A. Exceptions can be made for infants, <12 months of age, if unable to fast for the full 4 hours. If a patient has any vitamin level(s)

that are outside of the reference range, vitamin supplementation adjustments may be required. Target ranges and supplementation strategy guidelines can be found in [Appendix 5](#).

A serum pregnancy test will be performed at Screening Visit 1. A urine pregnancy test will be collected at all other visits for females who have reached menarche. If a urine pregnancy test is positive, a serum pregnancy test is to be performed to confirm the pregnancy. Study drug administration will be held pending the confirmatory results. If the serum pregnancy test is negative, the patient can resume dosing. If the serum pregnancy test is positive, the patient is to be discontinued (see [Section 10.2.9](#)).

All samples will be processed and transported to a laboratory per instructions in the laboratory manual. For the purposes of study conduct, only laboratory tests done in the central laboratory may be used. Local laboratories may be used at the discretion of the local investigator for management of urgent medical issues. If a local laboratory test value is found to be abnormal and clinically significant, it will be verified by the central laboratory as soon as possible after the investigator becomes aware of the abnormal result. If it is not possible to send a timely specimen to the central laboratory (e.g. the patient was hospitalized elsewhere), the investigator may base the assessment of an AE on the local laboratory value.

The observed laboratory values will be recorded and assessed according to the investigator’s clinical judgment.

Additional safety blood samples may be needed due to follow up of an abnormal value or analysis failure. The blood samples collected for safety laboratory analysis will be destroyed after the analyses have been completed.

**Table 4 Routine Laboratory Parameters**

Clinical Chemistry	Hematology	Urinalysis

 
• Albumin
 
• ALT
 
• Alkaline phosphatase (and isoenzymes as applicable)
 
• AST
 
• Bilirubin – total and direct
 
• Calcium
 
• Chloride
 
• Cholesterol
 
• Creatinine
 
• Creatine kinase
 
• Gamma-glutamyl transferase
 
• Potassium
 
• Sodium
 
	
 
• Hematocrit
 
• Hemoglobin
 
• Platelet count
 
• Red blood cell count
 
• White blood cell count and differential (neutrophils, eosinophils, basophils, lymphocytes, and monocytes)
 
	
 
• Blood
 
• Glucose
 
• Ketones
 
• Leukocytes
 
• Nitrites
 
• pH
 
• Protein
 

ALT = alanine aminotransferase; AST = aspartate aminotransferase.

**10.2.2 Individual Patient Safety Monitoring**

**10.2.2.1 Liver Monitoring**

Strategies to monitor markers of liver disease throughout the study are outlined below where the ULN will be based on central laboratory reference values for age and gender.

The liver monitoring criteria for study drug interruption are provided in [Table 5](#). If any of the ALT, AST, bilirubin, and alkaline phosphatase criteria are met, repeat testing must be performed within 48 to 72 hours. If the criteria are confirmed upon repeat testing, study drug must be interrupted immediately.

Study drug must be interrupted immediately without waiting for confirmatory testing if any of the INR or symptom-based criteria are met in [Table 5](#).

**Table 5 Liver Monitoring - Study Drug Interruption Criteria**

Laboratory value(s) or Symptoms	Interruption Criterion
AST or ALT in combination with total bilirubin (confirmed with repeat testing within 48 to 72 hours)	CCI
Total bilirubin (confirmed with repeat testing within 48 to 72 hours)	
INR	
Symptoms	

Symptoms	CCI
For patients <math>\geq</math> 18 years of age only	
Alkaline phosphatase in combination with direct (conjugated) bilirubin a (confirmed with repeat testing within 48 to 72 hours)	

ALT = alanine aminotransferase; AST = aspartate aminotransferase; INR = international normalized ratio; ULN = upper limit of normal.

aIf the alkaline phosphatase is confirmed to be NOT of liver origin (e.g. of bone origin) with the use of alkaline phosphatase isoenzymes, this criterion is not applicable.

If study drug is interrupted due to one of the criteria in [Table 5](#):

- a. Initiate drug-induced liver injury work-up for alternative etiologies
- b. Repeat liver profile (AST, ALT, total bilirubin, direct bilirubin) and prothrombin time or INR within 48 to 72 hours
- c. Monitor the patient using close observation found in [Section 10.2.2.2](#)
- d. If a patient resides in a remote area, they may be tested locally and the results communicated to the investigator site promptly. Results of any local liver-related laboratory tests and normal ranges must be shared with the medical monitor in a timely fashion

#### 10.2.2.2 Close Observation

- Repeat liver enzyme and serum bilirubin tests 2 or 3 times weekly. Frequency of re-testing can decrease to once a week or less if abnormalities stabilize or the trial drug has been discontinued and the patient is asymptomatic
- Obtain FGF19, p-C4, and pharmacokinetic levels within 3 days (p-C4 and PK only for patients  $>10$  kg)
- Obtain a more detailed history of symptoms and prior or concurrent diseases

- Obtain a history of concomitant drug use (including non-prescription medications and herbal and dietary supplement preparations), alcohol use, recreational drug use, and special diets
- Consider ruling out alternate etiology including acute viral hepatitis types A, B, C, D, and E; autoimmune or alcoholic hepatitis; non-alcoholic steatohepatitis; hypoxic/ischemic hepatopathy; and biliary tract disease
- Obtain a history of exposure to environmental chemical agents
- Obtain additional tests to evaluate liver function, as appropriate (e.g. INR, direct bilirubin)
- Consider gastroenterology or hepatology consultations and liver biopsy

#### **10.2.2.3 De-challenge/Re-challenge for Liver and Clinical Hepatitis Monitoring**

1. Re-challenge is not recommended:
  - a. If a patient has had possible/probable drug-induced liver injury
  - b. If a decompensation event has occurred (see [Table 5](#) for definition)
2. If due to underlying cholestatic liver disease variability or another alternative etiology is identified AND liver tests returned to baseline, re-challenge may be considered. The sponsor Medical Monitor must be notified prior to re-challenge
3. If the ALT/total bilirubin elevations are observed after re-challenge, then repeat re-challenge is discouraged

If patient is permanently discontinued, monitoring is to be continued as outlined in [Section 10.1.3](#).

#### **10.2.2.4 Diarrhea**

Study drug is to be interrupted if a patient develops diarrhea with at least 1 of the following concomitant signs or symptoms: grossly bloody stools, vomiting, dehydration requiring treatment with oral or intravenous rehydration and/or electrolyte imbalances, fever ( $\geq 38$  C) and/or the diarrhea persists for 7 or more days.

If there is gross blood in stool, INR and platelets are to be measured.

Study drug will be reintroduced (re-challenge) when the symptoms have resolved. If the diarrhea re-occurs within 1 week after the re-challenge with no alternate etiology, the dose of study drug can be reduced to 40  $\mu\text{g}/\text{kg}/\text{day}$  ([Section 8.3](#)). If the diarrhea persists on the lower dose of study drug, the patient will be permanently discontinued and monitored as outlined in [Section 10.1.3](#).

Any dose modification must be recorded in the clinical database.

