### 7.2.4 Individual Patient Stopping Criteria

While this study has no restrictions on patient age at enrollment, it is likely that the majority will be in the pediatric age categories. To protect the patients, administration of study drug will be stopped for the following reasons:

- An AE that, in the opinion of the investigator, necessitates treatment discontinuation. Specific instructions for the management of hepatic AEs, potential drug-induced liver injury and diarrhea are provided in [Section 10.2.2](#)
- In the opinion of the investigator there is no longer a potential benefit for continuing treatment; for example in patients who develop hepatic failure requiring liver

transplantation or in patients who undergo biliary diversion surgery for the relief of pruritus

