### 8.3 Dose Modification Guidelines

If, in the clinical opinion of the investigator, a dose modification may be beneficial to manage any potential AEs, dose modification is permitted and study drug may be continued at a reduced dose level of 40 µg/kg/day (Table 3). In addition, if study drug is interrupted for clinically significant diarrhea (Section 10.2.2.4) and the patient fails re-challenge at 120 µg/kg/day, the patient may be re-challenged at 40 µg/kg/day. With the exception of clinically significant diarrhea, the timing of dose increase/re-challenge at 120 µg/kg/day is at the discretion of the investigator. Two dose reductions are permitted during the study. Any dose modification must be recorded in the clinical database.

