### **10.3 Individual Study Drug Interruption and/or Discontinuation**

Study drug administration will be discontinued for the following:

- CTCAE Grade 3 or higher deemed possibly or probably related to study drug by the site Investigator.
- CTCAE Grade 4 or higher regardless of attribution to study drug.

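### Protocol 10.2.2.4 (re-challenge after diarrhea) and 10.3 (discontinue for Grade 3 or higher) can apply to the same event with no stated precedence, and 10.3 leaves out definitely related events

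*Protocol*

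**What the plan says.** **Protocol 10.2.2.4 (Diarrhea).** Study drug is interrupted for diarrhea accompanied by listed signs or lasting at least 7 days. One listed sign is "dehydration requiring treatment with oral or intravenous rehydration and/or electrolyte imbalances". The next step is "Study drug will be reintroduced (re-challenge) when the symptoms have resolved". If diarrhea returns within a week with no other cause, the dose can be reduced to 40 µg/kg/day. The section requires a permanent stop only if diarrhea persists on that lower dose. Neither CTCAE grade nor causality conditions the re-challenge.

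**Protocol 8.3 (Dose Modification).** This section builds on the same sequence: "if study drug is interrupted for clinically significant diarrhea (Section 10.2.2.4) and the patient fails re-challenge at 120" µg/kg/day, re-challenge at 40 µg/kg/day is permitted. It does not mention 10.3.

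**Protocol 10.3.** The lead-in is "Study drug administration will be discontinued for the following", and two criteria come after it. The first depends on attribution: "CTCAE Grade 3 or higher deemed possibly or probably related to study drug by the site Investigator". The second applies whatever the cause is judged to be: "CTCAE Grade 4 or higher regardless of attribution to study drug".

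**Protocol 7.2.4 (Individual Patient Stopping Criteria).** "Specific instructions for the management of hepatic AEs, potential drug-induced liver injury and diarrhea are provided in" Section 10.2.2. This section does not mention 10.3 either.

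**Protocol 10.1.2.4 and 10.1.2.5.** The severity scale includes "Grade 3: Severe or medically significant but not immediately life-threatening; hospitalization or prolongation of hospitalization indicated". The causality scale counts three levels as related: possibly, probably and definitely.

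**The concern.** Both rules are written as instructions, and they point in opposite directions for the same child. A site that follows 10.2.2.4 re-exposes the child once symptoms clear. A site that follows 10.3 stops drug. Section 5.5 expects loose stools or diarrhea from the mechanism of action, so attribution to study drug is plausible. SAP Table 6 has its own selection for diarrhea of CTCAE Grade 3 or higher, so the sponsor has allowed for the category.

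What is at stake is consistent safety conduct across sites: whether a child with severe, drug-attributed diarrhea is given study drug again should not depend on which section the site reads. The causality wording in 10.3 is a separate defect. It would be present even if precedence were clear.

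**Working it through.** No sample size, power or rate enters this point, so the check is a comparison of texts. Take a diarrhea event that meets a 10.2.2.4 trigger and has resolved, and apply each section literally.

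| Event | 10.2.2.4 | 10.3 | Result |
|---|---|---|---|
| Grade 1 or 2 | re-challenge | silent | no conflict |
| Grade 3, unlikely related or unrelated | re-challenge | silent | no conflict |
| Grade 3, possibly or probably related | re-challenge | discontinue | conflict |
| Grade 3, definitely related | re-challenge | silent as worded | re-challenge stands unopposed |
| Grade 4, any attribution | re-challenge | discontinue | conflict |

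1. **The overlap is real.** Dehydration needing intravenous rehydration is a 10.2.2.4 trigger. If admission is indicated for it, the event also meets the Grade 3 description in 10.1.2.4. One event can therefore satisfy both sections.

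2. **The overlap is partial.** Vomiting, fever or oral rehydration also trigger 10.2.2.4, and none of these implies Grade 3. Most of the range of 10.2.2.4 is untouched by 10.3.

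3. **Nothing sets precedence.** 10.2.2.4 does not cite 10.3, and 10.3 does not cite 10.2.2.4. Section 7.2.4 sends diarrhea management to 10.2.2, which leans towards re-challenge but does not say that it overrides 10.3. Section 8.3 assumes that re-challenge at 120 µg/kg/day has happened. It also excepts clinically significant diarrhea from the investigator's discretion over the timing of that step.

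4. **The other restart rules are softer.** Liver re-challenge (10.2.2.3) is something that may be considered, is not recommended after possible or probable drug-induced injury, and needs prior notice to the Medical Monitor. Restart after a vitamin interruption (10.2.2.5) is left to the investigator. Only the diarrhea rule is worded as an instruction to restart with no condition beyond resolution.

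5. **The causality gap is narrow.** Grade 4 and above is covered whatever the attribution, so the omission affects Grade 3 events judged definitely related. There the literal result is perverse: a possibly related event stops drug and a definitely related one does not. SAP 4.8.1 uses all three levels for drug-related events, so the two-level wording in 10.3 looks like a slip.

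**The case against.** **The investigator can always stop.** Section 7.2.4 requires a stop for an AE that the investigator judges to need it. Section 7.1.4 allows permanent discontinuation at any time in the patient's interest. Section 8.3 allows continuation at 40 µg/kg/day to manage AEs. This stands, and it limits the harm: a reader might infer that a site is compelled to re-expose a child it considers unsafe to re-expose, and the documents do not support that. It leaves open which instruction applies when the investigator does not use that authority.

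**The two rules can be reconciled.** The heading of 10.3 covers interruption as well as discontinuation, and its text does not say the stop is permanent. Sections 7.1.4, 10.2.2.4 and 10.2.9 do say so where they mean it, and 10.1.4 lists temporary discontinuation as an action for an SAE. On that reading 10.3 stops drug by grade and 10.2.2.4 supplies the restart for diarrhea. The pointer in 7.2.4 supports treating the specific rule as governing. This reading is tenable, so a flat contradiction cannot be claimed. But 10.3 gives no restart path, and a site has to infer the harmony from a heading and a missing word.

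**Wider consequences do not follow.** A reader might infer that the 10.4 trigger is distorted. It is not: 10.4 counts attributed Grade 3 events whatever is done next. A reader might infer that the safety tables become unreliable. The SAP's interruption and discontinuation tables record the action taken, and events of Grade 3 or higher and clinically significant diarrhea are tabulated regardless of action. Efficacy data after treatment discontinuation are retained under the treatment policy strategy (SAP 4.5.2).

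**No frequency can be supported.** It is tempting to attach a probability that some child will fall under both rules. Section 5.5 reports one diarrhea AE in the pediatric Phase 2 study without a grade, so any rate would be invented. Sites also apply the rules blinded to all 45 planned children, so the active arm alone would be the wrong base.

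**Conclusion.** The point holds as a gap in two safety instructions. For resolved diarrhea that meets a 10.2.2.4 trigger and is either Grade 3 and possibly or probably related, or Grade 4, the protocol gives two instructions and does not rank them. Independently, 10.3 as worded does not reach a definitely related Grade 3 event.

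The size is modest. It concerns a subset of diarrhea events whose frequency the documents do not give, investigator discretion guards against the worst outcome, and no effect on efficacy, power or the 10.4 count is claimed. The conclusion rests on two readings: that Grade 3 is assigned as 10.1.2.4 describes it, and that the verb in 10.3 means more than a pause. If the sponsor confirms that 10.3 intends only a pause, the precedence question is answered, but the text should then say so. Which rule ought to prevail is partly a sponsor choice; the documents do not compel one direction.

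**What to change.** 1. **10.3:** change the first criterion to cover events that are *possibly, probably or definitely related*.
2. **10.2.2.4 and 8.3:** make re-challenge subject to 10.3. In 10.2.2.4, add after the re-challenge instruction *unless the event meets the discontinuation criteria in Section 10.3*. In 8.3, open the diarrhea sentence with *Subject to Section 10.3*.
3. **Alternative to 2:** if the sponsor intends re-challenge after resolved Grade 3 diarrhea, state that exception in 10.3.

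Do not make the stop in 10.3 explicitly permanent as part of this edit. The restart rules in 10.2.2.3 and 10.2.2.5 also carry no grade limit and would have to be aligned first.

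**Cost.** Three sentences and a note to sites, with no new procedure; a child who stops has the EOT visit already defined in 7.1.4. The clinical cost of option 2 is that some children who might have tolerated re-challenge or 40 µg/kg/day would stop study drug. That includes a child with unrelated Grade 4 diarrhea, whom 10.3 already covers. SAP 1.1 describes enrollment as complete, so the practical benefit is limited to children still on treatment.
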